				12.0 Error! Bookmark not defined.1
				13.0 Error! Bookmark not defined.15-1
13.1	Error! Bookmaı	k not defined		13.0 End: Bookmark not denned.13-1
_				
13.2	Error! Bookmai			
13.3	Error! Bookmai	k not defined.		
				14.0 1916-1
Append	ices			1

AT2 in Kidney Transplant Page 3 of 22

LIST OF ABBREVIATIONS

ADE Adverse Drug Event
AE Adverse Event
AKI Acute Kidney Injury
ATN Acute Tubular Necrosis

BP Blood Pressure

CrCl Calculated Creatinine Clearance (via Cockcroft Gault equation)

DBP Diastolic Blood Pressure

RAAS Renin-Angiotensin-Aldosterone system

EKG Electrocardiogram

GFR Glomerular Filtration Rate
KDPI Kidney Donor Profile Index
MAP Mean Arterial Blood Pressure
PHI Protected Health Information

SBP Systolic Blood Pressure

HR Heart Rate

SCr Serum Creatinine

UIHHSS University of Illinois Hospital and Health Sciences System
HIPAA Health Insurance Portability and Accountability Act

PHI Protected Health Information

PI Principal Investigator

1.0 PROJECT SUMMARY/ABSTRACT:

The current standard of catecholamine vasopressor management of perioperative hypotension in kidney transplant patients carries significant risks and falls short in many ways. Currently, there is an absence in the scientific literature and research describing the hemodynamic effectiveness and safety of novel pharmacologic agents such as angiotensin II (Giazpreza – Ang II) in perioperative kidney transplant patients. Phase 3 registrational trials have demonstrated the superior safety and efficacy of Ang II (Giapreza) in distributive shock patients compared to traditional vasopressor agents and the novel mechanism of action may provide additional protection in renal transplant patients. The pilot study entails giving informed and consenting kidney transplant recipients Ang II (Giapreza) as their first vasopressor if the need for vasopressors emerge either intraoperatively or postoperatively in kidney transplant recipients. The primary objective is to evaluate the safety and hemodynamic effects of Ang II (Giapreza) in the renal transplant population.

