
The following section is designed to describe the current peri-op processes of renal transplant patients at UI Health in order to clearly delineate how this specific research protocol will deviate from the standard of care.

The normal care process for deceased donor kidney transplants (DDKT) at University of Illinois Hospital and Health Sciences (UIHHSS) includes the following:

PRE-TRANSPLANT

- Patient is end-stage renal disease (ESRD) on dialysis meeting set criteria for kidney transplant
- Patient obtains medical and social clearance for kidney transplant including blood tests (SCr, LFTs, Thyroid studies, CBC w/ diff); Diagnostics: chest X-ray; Cardiac clearance: ECHO, ECG, +/- Stress test, +/- Left heart cath; Cancer screening: colonoscopy, skin CA screening, prostate exam (if applicable), gynecological exam (if applicable); pregnancy screening (if applicable); Surgical clearance; and Nephrology clearance
- Once cleared, patient is listed with our institution and placed on our waitlist
- Patient has yearly check-in visits to re-evaluate if still eligible for transplant and medically able to obtain transplant
- If kidney becomes available, patient is notified to urgently come to either the UIHHSS Surgicenter or Emergency Room to be expeditiously admitted to the OR for their transplant (this time is generally limited to 1-3 hours)
 - It should be noted that time is of extreme value as longer time that passes before implantation of donor kidney has been associated with worse renal outcomes in recipient

DURING TRANSPLANT

- The transplant operation begins.
- If intraoperative hypotension occurs (e.g. SBP < 120 mmHg) the attending surgeon and attending anesthesiologist will:
 - Give blood products first if patient bleeding
 - If not bleeding or hypotensive despite blood products, intravenous fluids will be given
 - If hypotensive despite intravenous fluids then the attending surgeon and attending anesthesiologist will assess for cardiogenic shock and if suspected give inotropes
 - If not in cardiogenic shock and hypotensive despite fluids (+/- inotropes) then catecholamine vasopressors will be given for the treatment of distributive shock.
 - Vasopressor medications will be titrated intraoperatively to achieve goal BP

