The study drug will be provided by La Jolla Pharmaceuticals for this study but they are not the study sponsor or providing any other financial support. Drug distribution will be managed by the Investigation Drug Service (IDS) at UI Health who has the capacity to retain all of the study drug in appropriate temperature-controlled settings. IDS will be used as this is a novel medication, not yet on formulary at UIHHSS, and this is a research investigation. They will maintain and dispense the medication for each kidney transplant in which subjects have consented in the event that vasopressors are required. Additionally, the medication will be ordered via Cerner/EPIC as a study medication and will be programmed into the Alaris pumps to be dosed via the dosing protocol listed above. Ang II (Giapreza) will not be used outside of the study protocol at our institution and will only be available under the electronic study order. Verifying pharmacists will be in-serviced regarding the study protocol and will be aware that this medication is only available and should be dispensed under the study order and as such not used in other contexts.

FOR STUDIES THAT COLLECT EXISTING OR PROSPECTIVE DATA

Health and laboratory data will be extracted manually from the electronic medical records (i.e. Cerner or Epic) for both arms of the study. Data will be prospectively captured over the course of 3 months after study initiation (i.e. using Ang II (Giapreza) for vasopressor management during kidney transplant) for the pilot. The data will be collected and input into a Redcap database for analysis. Data analysis will be performed using Spss.v25 computer software. Data collection will include the variables below.

Baseline characteristics:

-Age (years of age at the time of transplant)

- -Gender (M/F)
- -Race
- A) White
- B) Black
- C) Asian
- D) Hispanic
- E) Other
- -Weight (kilograms at time of transplant)
- -Height (centimeters at time of transplant)
- -Body mass index (kg/m² at time of transplant)
- -Duration of time on hemodialysis (years)
- -Donor baseline serum creatinine (mg/dL)
- -Warm/cold ischemia time (hours)
- -KDPI
- -Baseline systolic/diastolic/mean arterial pressure (mmHg)
- -Baseline heart rate (HR)
- -Comorbidities
- A) Hypertension
- B) Hyperlipidemia
- C) Heart failure with preserved ejection fraction
- D) Arrhythmias
 - -Atrial fibrillation
 - -Other
- E) Peripheral vascular disease
- F) Coronary artery disease
- G) Pulmonary hypertension
- H) Diabetes

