- -Induction immunosuppression regimen
- -Maintenance immunosuppression regimen
- -First SCr, CrCl, calculated GFR after operating room (mg/dL)
- -Daily SCr, CrCl, calculated GFR after operating room (mg/dL)
- -Average SCr, CrCl, calculated GFR during hospitalization (mg/dL)
- -First serum lactate after operating room (mmol/L)
- -Peak serum lactate after operating room (mmol/L)
- -Duration of elevated (> 2 mmol/L) lactate after operating room (mmol/L)
- -Discharge SCr, CrCl, calculated GFR from hospital (mg/dL)

- -1-month SCr, CrCl, calculated GFR, 3-month SCr, CrCl, calculated GFR
- -Postoperative diuretic utilization (total milligrams of furosemide equivalents)
- -Postoperative midodrine usage (total milligram during hospitalization), duration of usage (days), used upon discharge (Y/N)
- -Postoperative mannitol utilization (Y/N)
- -Baseline serum albumin (mg/dL)
- -Need for renal replacement therapy in the first year after transplantation (Y/N)
- -Mortality during hospital admission for kidney transplant
- -Presumed or definitive allograft rejection rate during hospital admission for kidney transplant
- -Biopsy needed to rule out rejection (Y/N)
- -Calcineurin inhibitor (in tacrolimus equivalents) serum level at 1 week, 1-month, 3-month, 6-month
- -Suspicion for other types of shock (e.g. sepsis, cardiogenic, hemorrhagic as noted in chart documentation)

Safety data points:

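### First and early daily CrCl and GFR are calculated before creatinine is steady, and neither a recipient pre-transplant creatinine nor dialysis dates are collected to correct for it

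*Combined protocol and SAP*

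**What the plan says.** The List of Abbreviations defines CrCl as "Calculated Creatinine Clearance (via Cockcroft Gault equation"). No equation is named for the calculated GFR.

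Section 6.0, under Post-operative Clinical Data Points, takes creatinine, CrCl and GFR together at each of these points:

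- the first draw: "First SCr, CrCl, calculated GFR after operating room (mg/dL")
- each day: "Daily SCr, CrCl, calculated GFR after operating room (mg/dL")
- the stay as a whole: "Average SCr, CrCl, calculated GFR during hospitalization (mg/dL")
- discharge
- follow-up: "1-month SCr, CrCl, calculated GFR, 3-month SCr, CrCl, calculated GFR"

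No rule sets aside values taken while creatinine is still moving or after a dialysis session. The first draw has no clock time.

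Section 2 describes the population: "Patient is end-stage renal disease (ESRD) on dialysis meeting set criteria for kidney transplant". It mentions recipient creatinine once, in the work-up before listing: "Patient obtains medical and social clearance for kidney transplant including blood tests (SCr, LFTs, Thyroid studies, CBC w/ diff").

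The baseline list in section 6.0 has "Donor baseline serum creatinine (mg/dL") and years on hemodialysis. It has no recipient pre-transplant creatinine and no time of last dialysis. Dialysis after transplant is one yes/no item covering the first year.

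**The concern.** Cockcroft-Gault turns a single creatinine into a clearance. The conversion is valid only when creatinine production and removal are in balance. In a dialysis patient who has just received a kidney they are not: creatinine is falling from a uremic level if the graft works, rising if it does not, or has just been lowered by dialysis. A clearance calculated then says more about how the patient arrived than about the graft.

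The Background makes kidney function part of the rationale. It cites delayed return of creatinine to normal as a harm linked to catecholamines, and it argues that angiotensin II may protect the kidney. The first days are where such an effect would be looked for. A fall from the recipient's own starting level is the natural early measure, and that starting level is not among the variables. Section 9.0 also plans a regression on a poor kidney outcome without defining it, so nothing prevents the early values from being used there. With 20 treated patients, a few misranked ones could matter.

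**Working it through.** The plan gives no figure to reproduce, so the check is a one-compartment creatinine model whose output is put into Cockcroft-Gault.

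**Assumptions (none is in the documents).** Man aged 50, 80 kg, distribution volume V = 48 L, starting creatinine C0 = 8 mg/dL, true clearance 60 mL/min from reperfusion.

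**Formulas.**
- Cockcroft-Gault: (140 − 50) × 80 / (72 × SCr) = 100 / SCr mL/min. The production rate this implies is 1 mg/min, or 1440 mg/day.
- Elimination rate: k = 60 × 1.44 / 48 = 1.8 per day.
- Steady creatinine: 100 / 60 = 1.67 mg/dL.
- Working graft: SCr(t) = 1.67 + (8 − 1.67) × exp(−1.8t), t in days.
- Graft with no function: SCr rises by 1440 mg / 480 dL = 3.0 mg/dL per day. Here it starts at 4 mg/dL, having been dialysed down from 8.

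| Time | Working graft SCr | Its CrCl (true 60) | Low by a factor of | Non-working graft SCr | Its CrCl (true 0) |
|---|---|---|---|---|---|
| 0 | 8.00 | 12.5 | 4.8 | 4.00 | 25.0 |
| 6 h | 5.70 | 17.5 | 3.4 | 4.75 | 21.1 |
| Day 1 | 2.71 | 36.9 | 1.6 | 7.00 | 14.3 |
| Day 2 | 1.84 | 54.4 | 1.1 | 10.00 | 10.0 |
| Day 5 | 1.67 | 60.0 | 1.0 | – | – |

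The order is wrong at time 0 and at 6 hours, and right by day 1. With a starting creatinine of 6 or 10 mg/dL, the working graft's 6-hour reading is 22.6 or 14.3.

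**Second set of assumptions.** Age 55, 80 kg, 48 L, so CrCl = 85 × 80 / (72 × SCr) = 94.4 / SCr and production is 1360 mg/day. The working graft truly clears 50 from a start of 10 mg/dL; the non-working graft starts at 5.
- At 2 h: 10.4 (SCr 9.05) against 18.0 (SCr 5.24), reversed.
- At 6 h: 12.7 against 16.5, reversed.
- At 24 h: 25.5 against 12.1, right order but about half the true 50.
- Working graft later: 41.2 at 48 h, 47.7 at 72 h, 49.9 at 120 h.

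**When the order corrects.** Working grafts clearing 30 to 60 from 8–12 mg/dL were compared with non-working grafts starting at 4–7 mg/dL. Without dialysis, the order corrected between about 2 and 24 hours.

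**After post-transplant dialysis.** Assume dialysis at 24 h removes 60%, with a draw 6 h later. A non-working graft starting at 5 to 8 mg/dL then reads 24.6 to 18.7. A working graft clearing 30 from 10 mg/dL reads 17.6, so the order reverses again. One clearing 50 reads 30.1, so it does not. With the session at 48 h there is no reversal against either.

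**Hospital average.** For the graft clearing 50, the mean CrCl at 2, 24, 48, 72 and 96 h is 34.9, which is 1 − 34.9/50 = 30% low.

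**What a baseline adds.** In the first model, the fall by day 1 is (8.00 − 2.71) / 8.00 = 66% from the pre-transplant level. From a first draw at 6 h it is (5.70 − 2.71) / 5.70 = 52%, because the first 2.30 mg/dL is missed. The non-working graft shows a rise over the same period.

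**The case against.** Several points on the other side stand.

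- **Size.** A reader might infer that every daily value is wrong several-fold. The table does not support that: the error is 4.8- and 3.4-fold at time 0 and 6 hours, 1.6-fold at day 1 and 1.1-fold at day 2. Reversed ranking belongs mainly to the first value and depends on the pair of patients compared.
- **Raw creatinine is kept.** A reader might infer that early recovery cannot be measured at all. Creatinine itself is collected at the first draw and daily, so a fall from the first post-operative value can be computed. What is lost is the part before that draw and any way to mark values lowered by dialysis.
- **Use in analysis.** A reader might infer that these values define the poor kidney outcome in section 9.0. The section does not define it. They could enter, but the plan does not say that they do.
- **Availability.** The creatinine in section 2 belongs to the clearance work-up before listing and could be long out of date. The documents do not show that an admission value exists in every chart.
- **Consequence.** Section 3.0 makes time to blood pressure goal the primary measure and adverse event incidence the secondary. ICU urine output, need for dialysis, and 1- and 3-month values also describe the graft. CrCl is arithmetic on collected fields, so listing it destroys nothing.

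These points limit the concern without removing it. The plan still asks for clearance figures at times when the equation does not apply, and leaves out the two items needed to interpret them.

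**Conclusion.** The concern holds in a limited form. The first post-operative CrCl and GFR mostly reflect the creatinine on arrival: they can be low by a factor of about 3 to 5 for a working graft and can place it below a graft with no function. Daily values run low for about one to two days and can mislead again after dialysis. The hospital average carries the same bias, about 30% in the example. The fall from the recipient's own pre-transplant level cannot be computed from the listed variables, and dialysis-lowered values cannot be identified.

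The sizes rest on assumed age, weight, distribution volume, starting creatinine and dialysis effect. The direction of the bias in a working graft needs only that creatinine starts above its eventual steady level. The primary and named secondary endpoints are unaffected.

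**What to change.** 1. Add to the baseline list the recipient's last creatinine before transplant, with its date and the time of last dialysis, from the chart where available. Where there is none, use the first post-operative creatinine as the reference and say so.
2. Record the dates of post-transplant dialysis in addition to the yes/no item.
3. For the first and daily in-hospital values, report creatinine and its percentage fall from that baseline at fixed days, with dialysis days flagged. Drop the in-hospital average of CrCl and GFR.
4. Report CrCl and GFR at 1 and 3 months in patients off dialysis, and at discharge only if creatinine is stable and the patient is off dialysis.

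The cost is a few more fields in a manual chart extraction and the loss of an in-hospital GFR figure that is not valid. No treatment, visit or blood sample changes.

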11.0 DATA AND SAFTY MONITORING

The study drug will be given by FDA approved dosing and used within label as perioperative hypotension (when systematically addressed as noted above) is a form of distributive shock. As with all FDA approved medications, adverse events are reported. Patients will be monitored according to standard monitoring for patients in the perioperative transplant and collection of ADE will focus on those found in clinical studies using Ang II (Giapreza). The safety endpoints that will be captured will include: incidence of intraoperative arrhythmias for those who receive study drug intraoperatively (confirmed via EKG, flowsheet, or note documentation), incidence of postoperative arrhythmias occurring while receiving study drug postoperatively (confirmed via EKG, flowsheet, or note documentation), incidence of digital or other peripheral/visceral ischemia occurring during hospitalization for kidney transplant (as noted in chart documentation), incidence of venous or arterial thrombosis occurring during the hospitalization for kidney transplant (captured by ultrasound or other diagnostic imaging), incidence of thrombocytopenia while receiving study drug (as defined as platelet count < 50,000), incidence of post-operative fungal infections prior to discharge (as documented by the clinical care team), incidence of delirium while receiving study drug (as documented by the clinical care team), incidence of insulin infusion utilization while receiving study drug, pH values in the ICU at 24hrs, 48hrs, and 72hrs (if available). All of the noted safety variables above are routinely monitored for as part of ICU care.

The researchers will assess relatedness of the event to the study drug and will make every attempt to obtain enough information about the event to do so. Relationship of any AE to the use of study drug will be based on available information, using the following definitions:

Not Related: Another cause of the event is most plausible; and/or a clinically plausible temporal sequence is inconsistent with the onset of the event relative to initiation of study drug; and/or a causal relationship is considered biologically implausible.

Possibly Related: An event that follows a reasonable temporal sequence from administration of the Ang II (Giapreza) and in the investigators estimation follows a response pattern to the drug, but that could readily have been produced by a number of other factors.

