Probably Related: An event that follows a reasonable temporal sequence from administration of the Ang II and there is a biologically plausible mechanism for Ang II (Giapreza) to cause or contribute to the AE and the event could not be reasonably explained by the known characteristics of the participant's clinical state.

For reporting purposes, both 'Possibly Related' and 'Probably Related' will be considered **Related**.

Adverse events will also be graded by severity according to CTCAE criteria.

- -Grade 1: Mild; Asymptomatic or mild symptoms; clinical or diagnostic observations only; intervention not indicated.
- -Grade 2: Moderate; Minimal, local or noninvasive intervention indicated; limiting age-appropriate instrumental activities of daily living.
- -Grade 3: Severe; Medically significant but not immediately life-threatening; hospitalization or prolongation of hospitalization indicated; disabling; limiting self-care activities of daily living.
- -Grade 4: Life-threatening consequences; urgent intervention indicated.
- -Grade 5: Death related to AE.

Given this is a clinical trial a Data Safety Monitoring Board (DSMB) will be established. This board will be composed of two Critical Care Pharmacists ([name] and [name]) with intimate knowledge of Ang II (Giapreza), vasopressors, Ang II (Giapreza) safety endpoints and no relationship to the conduct of the trial. This DSMB will review the safety endpoints collected above after 5, 10, 15, and 20 subjects are enrolled. They will be provided a Safety Summary Report for the allotted number of patients with "Relatedness" and Grading of captured ADE as described above.

Study Halting Criteria: For existing participants study drug will halt dosing immediately until further safety analysis and assessment by the DSMB can be completed and no further enrollment will take place until approved by the DSMB. The halting criteria are as follows:

- Two participants experience the same Grade 4 adverse event considered related to study drug
- 20% of the participants at time of analysis experience the same Grade 3 adverse event
- One participant experiences a Grade 5 AE considered related to study drug

Study can be restarted if the DSMB says it is okay to continue.

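### In-hospital death, rejection and renal replacement therapy are collected but are not on the safety list the DSMB reviews, so some of these events need not reach it

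*Combined protocol and SAP*

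**What the plan says.** Under Post-operative Clinical Data Points, Section 6.0 lists "Mortality during hospital admission for kidney transplant", "Presumed or definitive allograft rejection rate during hospital admission for kidney transplant" and "Need for renal replacement therapy in the first year after transplantation (Y/N").

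The safety endpoints form a separate list, given in the same terms in Section 6.0 (Safety data points) and Section 11.0. It has nine items: intraoperative arrhythmias, postoperative arrhythmias, peripheral or visceral ischemia, venous or arterial thrombosis, thrombocytopenia, fungal infection, delirium, use of an insulin infusion, and pH. Section 11.0 introduces it by saying that "collection of ADE will focus on those found in clinical studies using Ang II (Giapreza").

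On oversight, Section 11.0 says: "This DSMB will review the safety endpoints collected above after 5, 10, 15, and 20 subjects are enrolled". On the report: "They will be provided a Safety Summary Report for the allotted number of patients", with relatedness and grade for the adverse drug events captured. On attribution: "The researchers will assess relatedness of the event to the study drug".

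The halting criteria in Section 11.0 are two participants with the same related Grade 4 event, 20% of participants with the same Grade 3 event (no relatedness condition), or "One participant experiences a Grade 5 AE considered related to study drug".

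**The concern.** Section 2 (Background) justifies the trial by linking perioperative catecholamines to delayed graft function, rejection and mortality, and names graft failure as the most serious consequence of missed blood pressure goals. The part headed Need for the Study says no data exist for this drug in renal transplant recipients, and Section 7.0 says most patients in the earlier Phase 3 trial had septic shock. The board's list therefore reflects what was seen in a different population and does not name the outcomes the protocol itself ties to vasopressor choice.

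The study has no concurrent control, so attributing one patient's death, rejection or dialysis to the drug is difficult. That is a reason for an independent board to see such events whatever the researchers conclude about cause. If it is not shown them, it could complete every scheduled review without knowing how many treated patients died, rejected the graft or needed dialysis.

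**Working it through.** The point rests on comparing passages of text. The plan states no figure to reproduce here: Section 12.0 says the sample is one of convenience, and no event rates are given.

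**Step 1. Match each outcome to the board's list.**

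| Outcome (Section 6.0, clinical list) | On the nine-item safety list? | Other written route to the DSMB |
|---|---|---|
| In-hospital death | No | In the report if it is a captured adverse drug event, such as a fatal listed event; through the halting rule if a Grade 5 event is judged related |
| In-hospital rejection | No | Only if recorded and graded as an adverse event |
| Renal replacement therapy, first year | No | Only if recorded and graded as an adverse event |

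None of the three is on the list.

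**Step 2. See what remains without a required route.** Nothing in Section 11.0 says that rejection or dialysis must be recorded as an adverse event. A death from an unlisted cause that is judged unrelated meets no halting criterion and belongs to no listed endpoint. Section 13.3 sends unforeseen problems to the IRB and does not mention the DSMB.

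**Step 3. Check timing.** The last scheduled review is at 20 enrolled, while renal replacement therapy is collected for a year after transplant. Dialysis starting after that review would miss every scheduled look even if it were on the list.

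**Step 4. How often might a death occur?** This is illustration only; the risks are assumptions. With 20 treated and a per-patient in-hospital death risk p, the chance of at least one death is 1 − (1 − p)^20:
- p = 1%: 1 − 0.99^20 = 18%
- p = 2%: 1 − 0.98^20 = 33%
- p = 5%: 1 − 0.95^20 = 64%

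These are chances that a death occurs, not that the board misses it.

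**Step 5. Would it be safe simply to count these outcomes under the halting criteria?** The 20% Grade 3 rule is met at 1 of 5, 2 of 10, 3 of 15 or 4 of 20. Suppose dialysis were graded 3 and affected 20% to 50% of recipients (both assumptions). The chance of at least one case among the first 5 is then 1 − 0.80^5 = 67% to 1 − 0.50^5 = 97%. Whether dialysis counts as an adverse event could therefore decide whether the study halts at the first review, and the plan leaves this open.

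**The case against.** A reader might infer more than the documents support, and four counter-arguments stand.

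- **Death reaches the board only if called related.** Not so. Relatedness is a condition of the Grade 4 and Grade 5 halting rules, not of the Safety Summary Report. A fatal thrombosis judged unrelated would still be reported, with its grade.
- **Attribution is the only filter, and the halting rules cannot see graft outcomes.** The Grade 3 rule has no relatedness condition. The halting rules refer to adverse events generally, Section 11.0 speaks of assessing any adverse event, and a focus on known events does not exclude others. The correct statement is that the board need not see these outcomes, not that it never would.
- **The safety list ignores the graft.** The items for visceral ischemia and for venous or arterial thrombosis on imaging cover the whole hospitalization and could capture graft ischemia or graft-vessel thrombosis.
- **A definite number of treated patients would have hidden graft events.** At an assumed early dialysis rate of 20% to 50%, the product with 20 patients is 4 to 10. That only restates the assumption, and the item collected is renal replacement therapy over a year, not early dialysis.

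Two other safeguards also limit the consequence: the treating physician may stop the drug for a safety concern (Section 6.0), and unforeseen problems go to the IRB (Section 13.3). Neither puts these outcomes before the DSMB. After all of this, there is still no text requiring rejection, dialysis, or an unrelated death from an unlisted cause to be reported to the board.

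**Conclusion.** The concern holds as a reporting gap. All three outcomes are collected, none is on the list the DSMB reviews, and for rejection, dialysis and unrelated deaths from unlisted causes no passage requires reporting to the board. This follows from the text alone and needs no assumed rate. How many patients it would affect cannot be derived from the documents.

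It does not follow that the DSMB would be unaware of drug-related deaths, or that the halting criteria are blind to graft harm. Nor do the documents support widening those criteria. Doing so would change when treatment stops, and on the assumptions in the working it would probably halt the pilot at its first review.

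This is an inexpensive improvement to oversight rather than a flaw that undermines the study.

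**What to change.** In Section 11.0, add three lines to the Safety Summary Report: all-cause in-hospital death, allograft rejection and renal replacement therapy. Each should be cumulative to the date of the review and reported whatever relatedness the researchers assign.

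Leave the halting criteria unchanged. The sponsor should reconcile the clinical data list in Section 6.0 with the adverse event, DSMB and halting text in Section 11.0, and state whether these outcomes count as adverse events under those criteria.

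The cost is a wording change and a few report lines. The data are already due to be extracted for every treated patient, though extraction must be up to date at each review. The sample size does not change. The one small downside is that expected early dialysis will appear in the report and the DSMB will have to put it in context.
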